6.4.3 Pregnancy during the study

Whenever it becomes known that a study subject or a partner of a study subject was pregnant during the exposure to study treatments, the outcome of the pregnancy, delivery, postpartum recovery and the clinical condition of the offspring during the neonatal period should be reported, subject to the study subject's or the partner's consent. A pregnancy follow-up form

will be provided to the investigator for completion after the sponsor has received the initial report.

Any case of pregnancy during a clinical study should be reported by the investigator in the same way as an SAE.

6.4.4 Clinical safety assessments

Pulse/heart rate, and systolic and diastolic blood pressure will be measured in a supine position after at least 5 minutes at rest before morning dose of study treatment at all study centre visits. For telephone contacts a pulse/heart rate assessment measured in a supine position after at least 5 minutes at rest before morning dose up to 3 days prior to the contact will be accepted.

Pulse rate will normally be assessed by manual palpation over at least 30 seconds by a qualified healthcare professional. Alternatively, mean heart rate as measured by the 12-lead ECG or a continuous ECG monitor may be used, however heart rate values measured by an automated sphygmomanometer are not accepted. Where possible, abnormal values should be re-checked (ensuring the subject is at rest) before making a decision concerning the levosimendan dose.

A standard 12-lead ECG will be recorded in a supine position after at least 5 minutes at rest at each centre visit during the treatment period, before the morning dose of the study treatment.

6.4.5 Laboratory safety assessments

A pregnancy test for female subjects of childbearing potential will be performed at baseline and at each study centre visit during the treatment period and at the end-of-study visit.

Local safety laboratory tests may be performed if clinically indicated (for example in assessment of an AE).

Instructions for the collection, handling, storage and transportation of samples will be provided before the start of the study.

6.4.6 Assessment of suicidality

Suicidality will be assessed by asking the following standard questions at each visit:

1. Since the last visit, have you wished you were not alive anymore or had any thoughts about ending your life?
2. Since the last visit, have you done anything or prepared to do anything to end your life?

The second question (2) will be asked only in cases where the answer to the first question (1) has been 'yes'.

6.5 Changes implemented due to COVID-19 pandemic

The following arrangements should be applied in the event that the subjects are not able to attend the study centre, either for baseline or treatment period visits, as a direct result of the COVID-19 pandemic.

All arrangements described in this section apply only to the extent that protocol requirements cannot be met because of COVID-19 restrictions. Study centre visits should take place to the extent possible and usual protocol requirements adopted for all subjects as soon as COVID-19 limitations permit. SVC and weight will not be assessed while these arrangements apply.

Exceptional measures taken in response to COVID-19 and their impact on study results, such as tests done in a local laboratory, will be explained, assessed and reported in the clinical study report following ICH E3.

Baseline visit

It will be possible for subjects to enter the study provided all eligibility criteria can be verified. In case baseline procedures described in [Table 1](#) and in section [6.1.1](#) cannot be performed at the study centre due to restrictions related to COVID-19, a telephone visit (could also be a home visit or video call) should be arranged (see table below). 12-lead ECG, laboratory safety assessments, pregnancy test and vital signs are essential for the evaluation of eligibility and must be obtained locally if they cannot be performed at the study centre.

All the eligibility criteria should be reviewed and discussed with the subject. In case all data needed to evaluate eligibility are not available, entry of the subject may be delayed until the tests can be performed.

Procedures at remote visits

Time	REFALS End-of-study visit	Visit 1 Baseline	Telephone visit to replace 3- monthly centre visit
IC (in case not collected at the study centre prior to the baseline visit)		x ¹	
Pulse/heart rate and BP (supine)	x ²	x ²	x ⁸
12-lead ECG	x ³	x ^{3,7}	x ³
Laboratory safety assessments ⁴			
Haematology	x	x ⁷	
Chemistry	x	x ⁷	
Urinalysis	x	x ⁷	
Pregnancy test for females of childbearing potential	x ⁵	x ⁷	x ⁵
Eligibility criteria and decision of entry		x	
Study treatment		x ⁶	x ⁶
ALSFRS-R		x	x
Borg CR10 scale	x	x ⁷	x
Use of health care and home care resources and non-medical assistive devices		x	x
Assessment of suicidality	x	x ⁷	x
Status for NIV support, invasive mechanical ventilation by intubation or tracheostomy and survival	x	x	x
AEs and SAEs	x	x	x
Medical history and current medical conditions			x
Concomitant treatments	x	x	x

¹ If IC is taken over the phone, it should be documented and confirmed by normal consent procedures as soon as possible.

² Performed in supine position after at least 5 min rest before the morning dose of the study treatment. The assessment should normally be done by a health care professional. The use of alternative methods, including home devices are subject to sponsor approval.

³ The measurement should be taken using the local ECG device after at least 5 min rest. A copy of the trace (paper or electronic) will be provided.

⁴ Standard biochemical, electrolyte and haematological test panels of the local laboratory will be accepted (at least Creatinine needed, exclusion criterion 4). A copy of the laboratory report with local reference range should be provided.

⁵ Test kits for urine pregnancy test should be provided to the subject for testing at home (unless taken in a local laboratory).

⁶ Study treatment shipped to subject's home.

⁷ Performed only in case not performed at REFALS end-of-study or study entry is delayed.

⁸ Performed locally.

Visits during the treatment period

During the treatment period any visit may be performed by telephone (see section 6.1.2). In case the first dose of study treatment is taken at the subject's home instead of the study centre,

arrangements should be made for the pulse rate to be measured before and 1 h after the first study treatment administration.

If the subjects are unable to attend the study centre at least once every 3 months, a specific telephone assessment as described in the table above should be performed. A 12-lead ECG recording should be performed along with blood pressure and heart rate measurement. A pregnancy test should also be obtained where applicable. In case these assessments cannot be obtained at the specified time, the benefit:risk ratio for the subject to continue in the study should be reassessed.

7. DATA COLLECTION AND MANAGEMENT

The investigators and study centre personnel will prepare and maintain accurate source data for each study subject about clinical findings specified in the protocol. Source data include patient records and laboratory results, if applicable. The data from source documents will be recorded into an electronic data capture (EDC) system, Medidata Rave (Medidata Inc), using eCRFs at the study centre. All data on the eCRFs must be verifiable in the source data or patient records unless eCRF data are declared as source data.

Investigators and other relevant study centre personnel will be trained to use the eCRFs. After completion of training, they are provided with user names and authorised access to enter and correct data on the eCRFs.

Electronic queries about missing, misleading, incomplete or illogical data will appear in the EDC system. An audit trail within the system will track all changes/corrections made. The investigator has to confirm the content of the eCRF with an electronic signature.

Individual data fields in the EDC system may be locked on an ongoing basis during the study. The fields may be unlocked if further updates are needed. When all data have been entered and all queries resolved, the whole database will be locked. Only authorised and well-documented updates to the study data are possible after the database lock.

An authorised person will code medical history, current medical condition and AEs using standard coding dictionaries. Prior and concomitant treatments will be coded.

Further details regarding data collection and management are presented in the data management plan.

Statistical analyses, tables and subject data listings will be performed with SAS[®] for Windows (SAS Institute Inc., Cary, NC, USA).

8. STATISTICAL METHODS

8.1 Statistical hypotheses

No formal hypothesis will be made

8.2 Estimation of sample size

No formal sample size calculation will be performed.

8.3 Analysis populations

All subjects who have received at least 1 dose of study treatment will be included into the analyses. Full analysis set will also include assessments from the REFALS study from participating subjects. Analyses will be performed with and without data from the REFALS study, depending on the analysis type.

8.4 Statistical analyses

Statistical analyses are described in more detail in the statistical analysis plan.

8.4.1 Demographic and other baseline characteristics

All relevant demographic and baseline characteristics will be summarised using descriptive statistics. The summary will be based on data collected at initiation of study 3119002 and covering all relevant changes prior to initiation of this study. The number and reasons for discontinuations will be listed and tabulated by treatment groups.

8.4.2 Treatment compliance and extent of exposure

The number of exposed subjects, the number of dispensed and returned study treatments and the duration of study treatment exposure will be tabulated with descriptive statistics.

8.4.3 Analysis of efficacy

Slope of decline in sitting and supine SVC and ALSFRS-R will be estimated using a random slope model. Estimation will be performed with and without the data collected in the REFALS study. When appropriate, between-subject comparisons will be performed using the randomised treatment arm in the REFALS study including a treatment-by-study interaction term.

Median time to NIV or death and to decline (by at least 1 point) in the ALSFRS-R respiratory domain will be evaluated using Kaplan-Meier estimates. Estimation will be performed with and without the data collected in the REFALS study. When appropriate, between-subject comparisons will be performed using the randomised treatment arm in the REFALS study, and Cox' proportional hazard regression model including treatment by study interaction term.

Borg CR10 (sitting, supine and orthostatic changes) will be evaluated using mixed model for repeated measures (MMRM) with and without the data collected in the REFALS study. When appropriate, between-subject comparisons will be performed using the randomised treatment arm in the REFALS study and appropriate MMRM including treatment by study interaction term.

Health and home care resource use data will be summarised in the study report, but any further analysis for potential pharmacoeconomic purposes will be reported separately.

To avoid selection bias in estimations, sensitivity analyses including all the subjects enrolled in the REFALS study will be considered. No imputation for missing data is planned. All efficacy data will be listed and summarised over time using appropriate descriptive statistics.

8.4.4 Pharmacokinetic analysis

In case PK samples are taken, levosimendan, OR-1855 and OR-1896 concentrations will be summarised using descriptive statistics. Metabolites OR-1855 and OR-1896 will be further summarised by subject acetylation status collected in the main study.

8.4.5 Safety analysis

8.4.5.1 Analysis of adverse events

AEs reported during the study will be classified by system organ class and preferred terms using the Medical Dictionary for Regulatory Activities (MedDRA) coding system. The AEs will be displayed as event counts and subject counts in a frequency table. The number and proportion (%) of subjects having each AE as well as the AE severity (mild, moderate, severe) and causality (related, not related) to the study treatment will be given. SAEs and other significant AEs will be evaluated case-by-case.

When appropriate, between-subject comparisons will be performed using the randomised treatment arm in the REFALS study. AEs reported as part of the REFALS study may be used to complement the safety profile.

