6.1.3 Additional visits

Additional centre visits or telephone contacts will be performed after changing the dose of the study treatment (see section [5.2.2](#)), approximately 2 weeks after the dose change. Procedures at these visits/contacts will be the same as described in [Table 2](#).

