7.9.2 Adverse events

Adverse events (AEs) will be classified by system organ classes (SOC) and preferred terms (PTs) using the MedDRA dictionary version 23.1.

A treatment-emergent AE (TEAE) is defined as any event arising or worsening after the start of study drug administration until 25 days after the last study medication intake.

A summary of TEAEs and non-TEAEs will be presented, showing total numbers of events and subjects having events:

1. Fatal outcome
2. SAE status
3. Other significant AEs
4. AESI status
5. Causality
6. Severity
7. Actions taken

The number of TEAEs, and number and proportion (%) of subjects having TEAEs by SOC and PT will be given by treatment group. The number of events will also be broken down by:

1. Severity (mild, moderate, severe)
2. Causality (related, not related)
3. Timing with respect to starting treatment (disjoint union of: ≤ 2 weeks, ≤ 4 weeks, ≤ 8 weeks, ≤ 12 weeks, ≤ 24 weeks, ≤ 48 weeks)
4. Dose change groups (see 7.4)

Incidence rates for subjects' first events adjusted for exposure time will also be reported. They are calculated by dividing the number of subjects ever experiencing the event while on treatment by the number of days subjects were exposed to the study treatment.

All serious adverse events (SAEs) and other significant AEs will be evaluated case by case. Narrative descriptions will be included in the study report for all AEs leading to death, other SAEs, AEs leading to study treatment withdrawal, and certain other significant AEs (OSAEs).

Groups of treatment emergent AEs of special interest (AESIs) are defined by Standardized MedDRA Queries (SMQs) where noted, and by in-house search categories (IHSCs) defined as lists of preferred terms, otherwise. Statistics for the following AESIs will be reported:

1. Asthenia or fatigue
2. Decrease in red cell parameters
3. Drug related hepatic disorders - comprehensive search (SMQ)
4. Haemorrhages (SMQ)
5. Headache
6. Hypokalaemia (SMQ)
7. Hypotension
8. Increased heart rate
9. Ischaemic heart disease (SMQ)
10. Neurocognitive disorder
11. Palpitations
12. Suicide/self-injury (SMQ)
13. Supraventricular tachyarrhythmias (SMQ)
14. Ventricular tachyarrhythmias (SMQ)

See Appendix 10.2 for the queries used to create the groups. If an SMQ has both a broad and a narrow definition, the narrow search will be used.

In addition to standard AE reporting, detailed characteristics will be reported for AESIs:

1. SAE status
2. Need for concomitant medications
3. Severity

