7.11 Changes from the clinical study protocol

Due to the results of the main study, and the consequent early termination of this extension study, the scope of reporting has been narrowed.

Most statistical analyses have been removed; instead, we report only descriptive statistics.

The analysis population is referred to as “safety population” rather than “full analysis set” for clarity, as the definition completely aligns with the safety population concept.

Protocol-defined reporting of REFALS baseline characteristics has been moved to additional analyses. Baseline characteristic reporting now reflects status at REFALS-ES baseline.

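### By SOC and PT, the SAP splits TEAE severity and causality by number of events only, so the number of subjects with a severe or related event of each type is not planned

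*Protocol*

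**What the plan says.** Protocol 8.4.5.1 sets the display for AEs: "The AEs will be displayed as event counts and subject counts in a frequency table". It continues: "The number and proportion (%) of subjects having each AE as well as the AE severity (mild, moderate, severe) and causality" to study treatment will be given. The synopsis says the same. Neither place states the counting unit for severity and causality.

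SAP 7.9.2 plans these displays:

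- An overall summary: "A summary of TEAEs and non-TEAEs will be presented, showing total numbers of events and subjects having events". Its list of rows includes causality and severity.
- A SOC and PT table: "The number of TEAEs, and number and proportion (%) of subjects having TEAEs by SOC and PT will be given by treatment group".
- A split of that table: "The number of events will also be broken down by" severity, causality, timing and dose-change group.
- More detail for the 14 AESI groups: "In addition to standard AE reporting, detailed characteristics will be reported for AESIs". Severity is on that list, without a unit. Causality is not on it.
- Narratives for deaths, other SAEs, withdrawals from treatment and certain other significant AEs.

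SAP 7.11 explains that reporting was narrowed after the main-study results and the early termination: "Most statistical analyses have been removed; instead, we report only descriptive statistics". It then names particular changes. The AE severity and causality tables are not among them.

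**The concern.** Evaluating long-term safety is the primary objective. For each type of event, a safety reader first wants to know what share of subjects had it, what share had it in severe form, and what share had it with a suspected link to the drug. The SAP supplies the first in subjects. For the other two, it changes the unit from subjects to events in the sentence that introduces the split.

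The subject count cannot be recovered from an event count, because several severe (or several related) events of one PT may belong to the same person. A row showing 10 severe events could describe one badly affected subject or ten. The two cases differ in meaning, and the planned SOC and PT tables cannot tell them apart.

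**Working it through.** The plan gives no figure for this point, so the check has two parts: which planned display gives which unit, and how far an event count leaves the subject count open.

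**1. Unit of each planned display (SAP 7.9.2)**

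| Display | Level | Unit for severity | Unit for causality |
|---|---|---|---|
| Overall summary | All events together | Events and subjects | Events and subjects |
| SOC and PT table | Each SOC and PT | Not split | Not split |
| Split of that table | Each SOC and PT | Events | Events |
| AESI detail | 14 groups | Not stated | Not listed |
| Exposure-adjusted first-event rates | Not split by severity or causality | None | None |
| Narratives | Single cases | Not a count | Not a count |

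No row clearly gives subjects by severity or by causality for each PT. The overall summary gives subjects, but only in total. It does not say whether a subject with both a mild and a severe event is counted in both severity rows or only in the worse one.

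Narratives do not close the gap. The protocol defines seriousness (6.4.1.1) separately from severity (6.4.1.2), so a severe or related event that is not serious has no assured narrative.

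**2. How much an event count leaves open**

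Input from the documents: the number of subjects who started the extension (SAP 7.1). The SAP's own flow reproduces: 329 − 28 − 54 = 247, and 247 − 20 = 227.

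Assumed input: e, the number of severe events of one PT. The same arithmetic holds for related events.

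Formula: e events come from at least 1 and at most e subjects, so the share of subjects lies between 1/227 and e/227.

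| e (assumed) | Fewest subjects | Most subjects | Share of 227 |
|---|---|---|---|
| 5 | 1 | 5 | 0.4% to 2.2% |
| 10 | 1 | 10 | 0.4% to 4.4% |
| 20 | 1 | 20 | 0.4% to 8.8% |

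**3. Whether the other planned columns narrow this**

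Take an assumed PT with 40 affected subjects, 60 events and 10 severe events. One subject can hold at most 60 − 39 = 21 of the events, so all 10 severe events may sit in one person. The planned table is then identical in these three cases:

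- 1 subject with severe events: 1/40 = 2.5% of those affected, 1/227 = 0.4% of all.
- 5 subjects: 5/40 = 12.5%, 5/227 = 2.2%.
- 10 subjects: 10/40 = 25.0%, 10/227 = 4.4%.

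In all three, the severe share of events is 10/60 = 16.7%. That figure does not identify the case.

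**The case against.** The strongest reply is that the protocol sentence does not require what is asked for. It states no unit for severity and causality and no cross-tabulation with subjects. Subjects per PT, plus severity and causality in some unit, is a permissible reading, and SAP 7.9.2 satisfies it. This stands as far as it goes: a breach of the protocol is not shown. However, the sentence follows directly on a commitment to both event and subject counts, so dropping subjects is narrower than its natural reading.

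A second reply is that much is covered elsewhere, through the overall summary, AESI detail, narratives and subject data listings. This also stands in part. A reader might infer that the SAP reports severity and causality by events everywhere. That is wrong, because the overall summary shows subjects too. The gap is confined to the SOC and PT level. Listings would allow a reader to count subjects by hand, but they are not a planned result.

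A third reply is that SAP 7.11 discloses a narrowed scope. The disclosure is general, and it speaks of replacing statistical analyses by descriptive statistics. Counts of subjects by severity are descriptive statistics, so it does not account for this omission.

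Two stronger inferences are tempting, and the documents do not support them:

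- A reader might think that repeated mild episodes hide severe ones. In a table split by severity, mild events fall in their own row and leave the severe count unchanged. They would lower only a severe share of events, and the SAP plans numbers of events, not such percentages, for this split.
- A reader might think that event counts are inflated by extra contacts, since "Additional centre visits or telephone contacts will be performed after changing the dose of the study treatment", or because the TEAE definition includes worsening. The standard AE question in Protocol 6.4.1.2 covers the whole time since the subject was last asked. The worsening clause defines treatment emergence and is not a rule for splitting records. How recurrent episodes are entered is not documented in either direction.

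**Conclusion.** The point holds in limited form. At SOC and PT level, the SAP plans severity and causality by number of events only. Subjects by severity and causality are planned in the overall summary alone, without a once-per-subject rule, and SAP 7.11 does not name the narrowing.

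The loss is that an event count gives an upper bound on the number of subjects and not the number itself. For 10 severe events of one PT, the share of the 227 subjects is known only to lie between 0.4% and 4.4%. The event counts used here are assumptions. The 227 is the SAP's own figure, taken as the safety population because those subjects are stated to have started the extension.

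The impact is modest. The study is descriptive and has no formal hypotheses, no estimate is biased by the omission, and the gap lies in table specification and not in data collection. It is worth closing because the change is nearly free and serves the primary safety objective.

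**What to change.** In SAP 7.9.2, under breakdown items 1 and 2, add by SOC, PT and treatment group:

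- the number and percentage of subjects by maximum severity of that event;
- the number and percentage of subjects with at least one related event.

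Count each subject once per PT (and once per SOC in the SOC rows), with the safety population of the treatment group as denominator. Keep the event counts beside them. State the same once-per-subject rule for the severity and causality rows of the overall TEAE summary. If the sponsor prefers events only at SOC and PT level, SAP 7.11 should list this as a change from Protocol 8.4.5.1.

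The cost is a few lines of SAP wording and one added column in tables already planned. Severity and causality are already recorded for every AE under Protocol 6.4.1.2, so no new data are needed.
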